9.1. Sample size for clinical implementation of Extubation Advisor

We will enroll a total of 72 patients, including patients both with and without COVID-19, able to provide informed consent, through a surrogate. We anticipate that 1 patient will be enrolled per week at each ICU (average of 24 patients per month), with enrolment occurring over a period of 3 months, and that there will be a 20% loss due to protocol deviation, loss of data, inability to provide a complete extubation CRF, etc. This will leave 58 patients with complete CRFs, which we anticipate 9-10 will experience extubation failure.

This will allow a robust evaluation of feasibility outcomes, including consent rates, waveform and clinical data collection, and report generation – see section 5 above). Over several months, individual clinicians will likely be in the ICU 3-5 weeks, and be exposed to 5-10 patients with EA, which we feel is adequate to provide their initial perceptions of usability.

9.2. Sample size for mixed-methods analysis.

We will interview up to 10-15 physicians and 10-15 respiratory therapists, distributed equally among participating sites, up to a maximum of 2 times. Repeated interviews will be conducted only when the study team deems the tool to have changed enough to warrant being seen again by the same people. Enrolment of 10-15 physicians and 10-15 respiratory therapists will be sufficient for thematic data saturation based on previous evidence supporting sizes of 10 to 13 participants in both theory-based and non-theory-based qualitative interviews^{34,35}.

10. Eligibility

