The secondary research objective of this study is to:

1. Evaluate the feasibility of completing the clinical case report form (CRF).

6. Study Outcomes

Primary objectives:

1. Implementation of Extubation Advisor will be considered feasible if:
 - a. >50% of identified eligible patients are enrolled and consented,
 - b. >75% of the time, wave form data is captured,
 - c. >90% of the time, participant clinical data is fully entered into the EA tool,
 - d. >80% of the time, an extubation report is successfully generated and delivered to the attending physician.
2. Usability, perceived value, identified behaviours, perceived barriers and drivers, and perceived impact will be assessed through interviews with RTs and MDs.

Secondary objectives:

1. Completion of the clinical CRFs will be considered feasible if >90% of clinical CRFs are complete.

7. Design

This is an open-label, multi-center interventional Phase 1 study to implement and evaluate perceptions of Extubation Advisor in consenting patients in the intensive care unit.

8. Centers

This study will be conducted at two Ontario academic hospitals: The Ottawa Hospital and Unity Health Toronto.

9. Sample Size and Timeline

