10.1. Inclusion and Exclusion Criteria for Patient Participants

Inclusion Criteria

Adult patients (≥ 18 years of age) with or without COVID-19 in the intensive care unit (ICU) able to provide informed consent (through a surrogate) and who meet the following criteria:

- Current invasive mechanical ventilation and anticipated to remain on invasive mechanical ventilation for at least 48 hours
- Ready for spontaneous breathing test (SBT) for assessment for extubation
- At least partial reversal of the condition precipitating mechanical ventilation
- Stabilization of other organ systems

- Tolerance of pressure support ventilation ≤ 14 cm H₂O, (oxygen saturation (SpO₂) $\geq 90\%$ with fraction of inspired oxygen (FiO₂) $\leq 40\%$ and positive end-expiry pressure (PEEP) ≤ 10 cm H₂O)
- Hemodynamic stability (low – phenylephrine < 50 ug/min; norepinephrine < 5 ug/min; dobutamine < 5 ug/kg/min; milrinone < 0.4 ug/kg/min – or no vasopressors)
- Stable neurological status (no deterioration in Glasgow coma score during prior 24 hours and, if measured, intracranial pressure (ICP) < 20 mmHg)
- Intact airway reflexes (adequate cough with suctioning and a gag reflex)

Exclusion Criteria

- Order not to re-intubate should the patient fail extubation
- Anticipated withdrawal of life support
- Known or suspected severe weakness (myopathy, neuropathy, or quadriplegia)
- Tracheostomy
- Prior extubation during current ICU stay

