10.2. Inclusion and Exclusion Criteria for Extubation Advisor Users

10.2.1 Inclusion and Exclusion Criteria for RT Users

Inclusion Criteria

Respiratory therapists who consent to participate in an interview and are the enrolled patient's:

- Respiratory therapist who has input data into the Extubation Advisor tool

Exclusion Criteria

- Respiratory therapist is unable to complete the interview in English

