10.2.2 Inclusion and Exclusion Criteria for MD Users

Inclusion Criteria

Physicians who consent to participate in an interview and are the enrolled patient's:

- Attending ICU physician and/or fellow

Exclusion Criteria

- Attending ICU physician or fellow is unable to complete the interview in English

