11.3. Study procedure for mixed-methods analysis

As the first phase in design and implementation of this complex intervention, we will conduct a series of short interviews with consenting respiratory therapists (RTs) involved in using the EA tool and critical care physicians (MDs) involved in extubation decisions for ventilated patients in the ICU, based on their experience of using EA and conducted within 96 hours of their actual patient extubation decisions.

In a general sense, these interviews will be designed to address Question #1 of the French Framework (‘Who needs to do what differently?’), obtain initial opinions about Question #2 (‘What barriers and enablers need to be addressed?’), and identify initial usability issues. Subsequent phases (the subject of a separate proposal) will involve more detailed evaluation of barriers to and drivers of EA usage using the Theoretical Domains Framework (Question #2)^{36,37}, assessment of optimal behaviour change techniques and modes of delivery (Question #3), and more formal UCD testing, both conducted in the context of a more formalized version of the tool.

All RTs and MDs will be informed that their participation in the study means they may be contacted by email to ask if they would be interested in participating in an interview. Potential interviewees (i.e. RTs/MDs who used the Extubation Advisor software and/or report) will then have their name and email address provided to the lead site to be contacted by the study team, consented, and asked to participate in a 15 to 30-minute interview within 96 hours of the patient extubation decision. The RT or MD may also provide their phone number to the lead site if they do not wish to conduct the interview via

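### Does section 9.1's expectation of 5-10 Extubation Advisor patients per clinician conflict with its accrual of one patient per ICU per week?

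*Combined protocol and SAP*

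**What the plan says.** Section 9.1 gives the accrual rate: "We anticipate that 1 patient will be enrolled per week at each ICU (average of 24 patients per month"). Enrolment lasts 3 months and totals 72 patients. The same section then turns to the users of the tool, whose weeks on service are spread over the study: "individual clinicians will likely be in the ICU 3-5 weeks, and be exposed to 5-10 patients with EA". The authors' judgement of that amount of experience is worded as an opinion: "which we feel is adequate to provide their initial perceptions of usability".

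Section 8 gives the setting: "This study will be conducted at two Ontario academic hospitals". The text available for review states neither the number of ICUs in those hospitals nor how many ICUs a physician or respiratory therapist (RT) covers.

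The users' perceptions are collected by interview. Section 10.2.1 admits an RT through one condition, "Respiratory therapist who has input data into the Extubation Advisor tool", and section 10.2.2 admits the enrolled patient's "Attending ICU physician and/or fellow"; each must also consent and be able to be interviewed in English. Under section 11.3 the interviews are "conducted within 96 hours of their actual patient extubation decisions". Section 9.2 sets their number at up to 10-15 physicians and 10-15 RTs, on saturation grounds.

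**The concern.** The rate, the weeks and the exposure range all stand in section 9.1, and on the most direct reading they do not multiply out. One patient a week for 3-5 weeks is 3-5 patients, so the derived and printed ranges meet only at 5, and the top of the printed range is double the derived top.

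The exposure range is also the reason section 9.1 gives for calling clinicians' experience adequate for a first view of usability, which belongs to the second primary objective. If the range were overstated by a factor of about two, clinicians' views would rest on less experience than the reader is told. Section 2.1 adds that the sites will decide after the 3 months whether to adopt the tool, so the depth of that experience is of real interest.

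**Working it through.** **Inputs.** From section 9.1: 1 patient per ICU per week, 24 per month, 72 over 3 months, 3-5 weeks per clinician, stated exposure 5-10. From section 8: two hospitals. From section 2.1: 151 spontaneous breathing trials (SBTs) in 117 patients in the earlier single-centre study. ICUs per clinician: not given.

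**1. The plan's own total.** ICUs implied = monthly accrual / weeks per month = 24 / 4 = 6, or 24 / (52/12) = 5.5. Six ICUs x 12 weeks x 1 per week = 72, which reproduces the sample size. Two ICUs would give only 2 x 12 = 24. The accrual figures therefore presuppose several ICUs per hospital.

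**2. Exposure by coverage.** Exposure = weeks x 1 per ICU-week x ICUs covered.

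| ICUs covered by one clinician (assumed) | 3 weeks | 5 weeks |
|---|---|---|
| 1 | 3 | 5 |
| 2 | 6 | 10 |
| 3 (a whole hospital, if six ICUs split evenly) | 9 | 15 |

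The rate needed for the printed range is 5 / 3 = 1.67 per week at the low end and 10 / 5 = 2.0 per week at the high end, that is, about 1.7-2 ICUs per clinician. The printed 5-10 lies within the 3-15 spanned by the table and close to the two-ICU row.

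**3. Counting reports instead of patients.** Section 11.1 allows a new report with each repeated SBT. At 151 / 117 = 1.29 SBTs per patient, one ICU gives 3 x 1.29 = 3.9 to 5 x 1.29 = 6.5 reports. This overlaps 5-10 but does not reach its top, and the sentence speaks of patients.

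**4. Patients already in progress when a clinician comes on service.** Patients enter when "Ready for spontaneous breathing test (SBT) for assessment for extubation", so only those awaiting a repeat SBT carry over. Repeat SBTs per patient = 1.29 - 1 = 0.29. With an assumed 1-3 days between SBTs, the mean time from first to last SBT is 0.29-0.87 days. Patients in progress at the start of a block = (1/7 per day) x 0.29 = 0.042, up to (1/7) x 0.87 = 0.125. If every week worked is a separate block in one ICU:

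- 3 weeks: 3 + 3 x 0.042 = 3.1 to 3 + 3 x 0.125 = 3.4
- 5 weeks: 5 + 5 x 0.042 = 5.2 to 5 + 5 x 0.125 = 5.6

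To close the gap by carry-over alone, each block would need 2 / 3 = 0.67 to 5 / 5 = 1.0 patient in progress, or a mean of 0.67 x 7 = 4.7 to 1.0 x 7 = 7 days from first to last SBT. On these assumptions carry-over is a small contributor. It is not excluded, because comparability with the earlier study is unknown.

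**5. What depends on the figure.** The sample size does not (step 1). The interview numbers rest on saturation evidence for 10-13 participants (section 9.2). Eligibility for interview needs one enrolled patient (section 10.2), and the interview works through an EA report (section 11.3). The four primary criteria and one secondary criterion in section 6 are proportions of patients, recordings, data entries, reports and forms; none uses exposure per clinician.

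**The case for a change.** The strongest case for a change is that 5-10 is the only ground section 9.1 offers for adequate exposure, and that the plan's accrual rate supports it only through an assumption it does not state. The wording speaks of the ICU in the singular, which favours one unit per clinician. The alternatives fall short too: counting reports or allowing for carry-over does not reach 10, and covering a whole hospital overshoots. Even 3-5 is generous, since it credits a clinician with every patient enrolled during those weeks, whereas an RT qualifies for interview only by having entered data personally. The repair would be one sentence.

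The multiplication stands, and so does the absence of a stated coverage figure in the text available for review, although some front matter was not available. Two things do not stand. The singular does not settle coverage, because section 4 uses the same singular for a study in several centres. And replacing 5-10 with 3-5 would exchange one underived range for another: it would assume one ICU per clinician, which the plan also does not say, and it would be wrong if clinicians cover two.

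**Conclusion.** No arithmetic error is shown. On one ICU per clinician the expected exposure is 3-5 new patients, which is 2 below the stated range at the low end and 5 below at the high end. On two ICUs it is 6-10, in practical agreement with 5-10. The plan does not say which applies, and its own total requires about six ICUs in two hospitals, so cover of more than one is a reasonable reading. All of this rests on the planned rate of one patient per ICU per week being met.

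The gap is missing background to a rough expectation, which the sentence marks as likely and as the authors' opinion. Even if the lower figure were right, enrolment, the number and content of the interviews, the analysis and the section 6 criteria would stay the same. Naming the number of ICUs and the cover per clinician would make the sentence easier to follow, but it would alter no result or conclusion. The plan can stand as written.

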10.1. Inclusion and Exclusion Criteria for Patient Participants

Inclusion Criteria

Adult patients (≥ 18 years of age) with or without COVID-19 in the intensive care unit (ICU) able to provide informed consent (through a surrogate) and who meet the following criteria:

- Current invasive mechanical ventilation and anticipated to remain on invasive mechanical ventilation for at least 48 hours
- Ready for spontaneous breathing test (SBT) for assessment for extubation
- At least partial reversal of the condition precipitating mechanical ventilation
- Stabilization of other organ systems

- Tolerance of pressure support ventilation ≤ 14 cm H₂O, (oxygen saturation (SpO₂) $\geq 90\%$ with fraction of inspired oxygen (FiO₂) $\leq 40\%$ and positive end-expiry pressure (PEEP) ≤ 10 cm H₂O)
- Hemodynamic stability (low – phenylephrine < 50 ug/min; norepinephrine < 5 ug/min; dobutamine < 5 ug/kg/min; milrinone < 0.4 ug/kg/min – or no vasopressors)
- Stable neurological status (no deterioration in Glasgow coma score during prior 24 hours and, if measured, intracranial pressure (ICP) < 20 mmHg)
- Intact airway reflexes (adequate cough with suctioning and a gag reflex)

Exclusion Criteria

- Order not to re-intubate should the patient fail extubation
- Anticipated withdrawal of life support
- Known or suspected severe weakness (myopathy, neuropathy, or quadriplegia)
- Tracheostomy
- Prior extubation during current ICU stay

10.2. Inclusion and Exclusion Criteria for Extubation Advisor Users

10.2.1 Inclusion and Exclusion Criteria for RT Users

Inclusion Criteria

Respiratory therapists who consent to participate in an interview and are the enrolled patient's:

- Respiratory therapist who has input data into the Extubation Advisor tool

Exclusion Criteria

- Respiratory therapist is unable to complete the interview in English

10.2.2 Inclusion and Exclusion Criteria for MD Users

Inclusion Criteria

Physicians who consent to participate in an interview and are the enrolled patient's:

- Attending ICU physician and/or fellow

Exclusion Criteria

- Attending ICU physician or fellow is unable to complete the interview in English

10.3. Co-enrolment

Given that this study is a feasibility and usability assessment, participant co-enrolment with other studies whose outcomes are unrelated to weaning and extubation will be permitted. We propose to allow co-enrolment with the Frequency of Screening and Spontaneous Breathing Trial Technique (FAST) RCT led by co-PI [name] even though it is directly related to weaning and extubation, for several reasons: the proportion of patients expected to be co-enrolled will be exceptionally small, the frequency

of SBT screening will not affect the EA assessment, and both arms of the SBT technique (no vent support vs minimal 5/5 PS/PEEP settings) are acceptable for an EA assessment as they represent variable institutional practice and were included in the original WAVE study. Thus, we have no limitations on co-enrolment.

11. Study Procedure

11.1. Study procedure for clinical implementation of Extubation Advisor (EA)

Eligible patients will be identified by RTs or Research Coordinators (RCs) in the ICU for SBT and assessment of extubation. A surrogate will be identified and contacted to provide informed consent on behalf of the eligible patient, after which the eligible patient will be enrolled. No formal screening log will be completed, and RTs/RCs will attempt to identify as many eligible patients as is feasible.

When an eligible patient is identified and enrolled, they will be connected to a bedside or portable monitor displaying ECG and capnography (and other waveforms). Capnography requires a CO₂ module in the monitor, connected to the endotracheal tube by capnography sampling tubing. The RC will first confirm that the patient monitor to be used is compatible with the EA software. An EA laptop will be connected to the monitor through a serial cable. The waveform and vital sign data will undergo processing directly on the laptop using the EA software.

An RT will prepare the patient for an SBT, making sure that the Capnograph (CO₂) module is installed on the monitor, that the CO₂ sensor is on the tubing prior to starting the SBT, and that a CO₂ signal is seen at the monitor. The RT will log on to the EA application and input the patient's demographic and admission information (one-time data entry performed in less than 2 min). The RT will then get feedback from the EA application that it is receiving the vital signs waveform data and that it includes a capnograph (CO₂) waveform (i.e. two separate but related requirements) and displays that the system is ready to go.

With the system indicating it is ready to go, the RT will press the “Start” recording button, initiating the waveform recording. They can then enter the starting (i.e. pre-SBT) ventilator (i.e. PS/PEEP values) and sedation score (i.e. RASS score) into the EA system (~20 sec). The RT will start the SBT by lowering PS/PEEP settings on the ventilator to whatever is ordered by the clinician and clicking the “Start SBT” button in EA to initiate the recording. While the waveforms are being recorded, the RT will complete the rest of the admission information, comorbidities, and extubation readiness checklist (<5 min). At the end of the SBT, the RT will stop the recording (or cancel the SBT if <15 minutes).

The EA system will process the portions of CO₂ waveforms and vital signs data corresponding to the SBT and proceed to clean and assess the quality of the data, compute variability metrics, and generate a score summarizing the risk of extubation failure.

The RT will then put the PS/PEEP back to normal on the ventilator and complete the SBT Outcome Information and their own impression of the risk of extubation failure (<2 min). The RT will click on the “Generate Report” button, which displays a PDF report on screen. The RT will then review the report with the attending physician and determine whether to proceed with the extubation or not. If desired, the EA report may be emailed to a secure hospital email with the actual report attached for printing, so that

the RT may physically give the report to the attending MD, or place it at the bedside. This process may be repeated every time an SBT is repeated for assessment of a patient’s readiness for extubation, until the patient undergoes planned extubation, or reaches an alternate outcome (self-extubation, direct to tracheostomy, death, transfer to another institution). RTs who complete EA data entry during the SBT will receive a \$10 coffee gift card, limited to a maximum of 3 gift cards per patient for repeated SBTs, as a token of appreciation for their time and expertise.

After a minimum of 72 hours after extubation, the site Research Coordinator will complete a short **Clinical Outcome CRF**, which will include the time of extubation, the outcome of extubation, the need and timing of re-intubation (if present), the need for non-invasive ventilation or high flow heated humidity, all within the 72 hours post-extubation. Last, the Clinical Outcome CRF will include the date of ICU discharge and the status of the patient at that time. Patients who remain hospitalized at 72 hours will be followed via their electronic medical record until hospital discharge.

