12.1. Feasibility evaluation of Extubation Advisor

To evaluate the feasibility of Extubation Advisor implementation we will quantify:

1. The number of identified eligible patients enrolled and consented to capture the proportion of both (a) patients enrolled and (b) patients not enrolled due to patient/caregiver refusal.
2. The proportion of useable recordings and data fully entered, and report on the reasons for failure.
3. The number of reports successfully generated and transmitted to physicians, and report on the reasons for failure.

To evaluate the feasibility of completing clinical CRFs we will quantify the number of clinical CRFs that have been deemed complete.

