For further information on the Mandatory Medical Device Problem Reporting by Industry, please refer to: *Guidance Document for Mandatory Problem Reporting for Medical Devices*.

14. Data Management

In order to predict the risk of extubation failure, the EA tool will be hosted on a Windows-based tablet or laptop with data acquisition software pre-installed and configured for the collection of vital sign waveform data from bedside monitors via a serial connection. Demographic and clinical data from patients enrolled in the study will be collected by respiratory therapists using the EA tool data entry interface in the intensive care unit.

Upon completion of data collection, automated algorithms will assess the quality of the waveform data, detect breaths, and perform cleaning of artifacts, missing data and noise, to form vital signs time series, which will be used to calculate variability metrics for the patient.

The resulting respiratory rate variability data will be fed into the trained EA predictive model, yielding a probability of extubation failure. A standardized checklist of clinical factors relevant to assess extubation readiness will be completed by the respiratory therapist via the EA user interface.

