The EA report will be generated within minutes and will be made available to critical care physicians to assist with extubation decision-making. The report will contain a risk estimate of extubation failure, a standardized extubation readiness checklist, vital signs, the best professional impression of extubation readiness by the respiratory therapist, and possible mitigation factors to consider prior to extubating a patient. Only the treating physician and respiratory therapist performing the SBT will have access to the Extubation Advisor (EA) report, containing Personal Health Information (PHI) and Personal Identifying Information (PII), unless the treating physician or respiratory therapist participants in an interview to evaluate EA. In these cases, the researcher from the lead site will be able to view the patient's PHI/PII on the EA report during the interview (name, date of birth, medical device identifier, MRN) but this information will not be stored by the lead site. Reports containing PHI and PII will temporarily be stored encrypted on a hospital approved laptop running the EA app. This data will be combined with waveform data captured during the SBT and patient outcome data collected via the Case Report Form to create the local study database, stored within the local hospital firewall on a secure, credentials-controlled server. The laptop will be password protected and the EA app will also require a username/password to access. The local study database will have identifying PII/PHI removed (name, date of birth, medical device identifier, and MRN) and replaced by unique patient and site identifiers using an automated script. Non-identifying PHI required to generate the EA report including age, sex and/or gender, admission date, discharge date, and date of death (if applicable) will remain in the study database. The link between the study IDs and identifying information will be maintained on the secure hospital server in a password protected excel file. Only the research personnel involved in this project will have access to this password protected file. The study database will be transferred to the lead site via secure upload, where all local study databases will be combined to create the final database for analysis.

The Dynamical Analysis Laboratory (DAL) at the Ottawa Hospital Research Institute will be responsible for monitoring and supporting EA software.

15. Study Management

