16.3. Monitoring and Audit

In accordance with Part 3 the *Medical Device Regulations*, and/or relevant ICH guidelines, the Sponsor or a designee will periodically inspect all completed study case report forms (see Section 10.4), study documents, research facilities, and clinical laboratory facilities associated with this study at mutually convenient times during and after completion of the study. The aforementioned responsibilities will be assumed by the regulatory correspondent, [name] at OHRI, or a designee.

As specified in the Study Monitoring Plan, the monitoring visits provide the Sponsor or the Regulatory Correspondent with the opportunity to evaluate the progress of the study; verify the accuracy and completeness of data in the completed case report forms; ensure that all protocol requirements, applicable Health Canada and other relevant regulations, and investigator's obligations are being fulfilled; and resolve any inconsistencies in the study records. This includes inspection of all documents and records required to be maintained by the investigator, including but not limited to medical records (office, clinic, or hospital) for the subjects in this trial. The names and identities of all research subjects will be kept in strict confidence and will not appear on electronic data entry forms or other records provided to or retained by the Sponsor or the Regulatory Correspondent. The investigator/institution guarantees direct access to source documents by the Sponsor and appropriate regulatory authorities.

The trial site may also be subject to review by the REB, to quality assurance audits performed by the Sponsor or the Regulatory Correspondent, and/or to inspection by Health Canada.

17. Investigational Testing Report

After closure of the investigational testing, the manufacturer or importer should submit a report of the study to Health Canada even if the investigation was terminated prematurely. This responsibility has been delegated to the Regulatory Correspondent.

- a. The report should include identification of the device, a description of the methodology and design of the investigation, any deviations from the protocol, data analysis together with any statistics and a critical appraisal of the aims of the investigation.
- b. The report should take into account the data from each investigation site and for all subjects. No subjects should be identifiable either from the investigation report or the published results.

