- c. Where applicable, the investigation testing report should be made available to the principal investigator and all investigators for review and comment. The sponsor and the Regulatory Correspondent shall maintain records confirming that the report has been provided for review. If a reviewer does not agree with all or part of the report, their comments should be recorded and communicated to the other principal investigators.
- d. The sponsor and coordinating investigator should provide their signatures, indicating their agreement with the content of the report. If no coordinating investigator is appointed, the signature of the principal investigators should be obtained.
- e. The report should be provided to the REB.

18. Record Retention

To comply with Health Canada regulations, the trial related records will be retained for 25 years. Records will be kept to enable linkage of participants' identity to CRF data (master log). This includes sufficient information from hospital and clinic records such as all original signed informed consent forms, source records, etc. After 25 years, all study records will be destroyed by shredding or incineration.

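### Primary criterion 1a and the refusal proportion need a count of identified patients who were not enrolled, but section 11.1 drops the formal screening log and no other source for that count is named

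*Combined protocol and SAP*

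**What the plan says.** The combined protocol and SAP treats enrolment and consent as the first of four primary feasibility criteria. Section 6, item 1a, requires that ">50% of identified eligible patients are enrolled and consented". Section 12.1, item 1, undertakes to report the "proportion of both (a) patients enrolled and (b) patients not enrolled due to patient/caregiver refusal".

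Section 11.1 sets the order of events: staff identify an eligible patient, a surrogate is contacted for consent, and the patient is then enrolled. On recording the first step it says: "No formal screening log will be completed, and RTs/RCs will attempt to identify as many eligible patients as is feasible".

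The patient-level records described elsewhere start at or after enrolment:

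- Section 11.1, outcome CRF: "After a minimum of 72 hours after extubation, the site Research Coordinator will complete a short" Clinical Outcome CRF.
- Section 14, EA data entry: "Demographic and clinical data from patients enrolled in the study will be collected by respiratory therapists".
- Section 14, the analysis data: EA and waveform data are joined with "patient outcome data collected via the Case Report Form to create the local study database".
- Section 18, retention: a master log linking participants to CRF data, and "all original signed informed consent forms, source records, etc".

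Section 16.2, on consent, mentions no record of refusals. Section 16.3 refers to a document that was not supplied: "As specified in the Study Monitoring Plan, the monitoring visits provide the Sponsor or the Regulatory Correspondent with the opportunity" to check progress and the case report forms.

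**The concern.** Criterion 1a and the refusal proportion share a denominator: enrolled patients plus identified patients who were not enrolled. The refusal proportion also needs the reason for each non-enrolment. The plan sets aside the usual source of this information and puts nothing named in its place.

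The two parts of the denominator are not equally well documented. An enrolled patient leaves a consent form and study data. A patient who was identified but whose surrogate declined, or was never reached, leaves a trace only if someone chose to write it down. Omissions therefore fall on one side of the fraction and push 1a towards a pass.

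Section 9.1 says the sample will support a robust assessment of consent rates among other outcomes, and the results are meant to inform a later randomized trial. The share enrolled and the reasons for non-enrolment are planning inputs for that trial, and they are hard to reconstruct afterwards if not recorded at the time.

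**Working it through.** **Inputs.** Planned enrolment is 72 (section 9.1), which reproduces as 24 per month × 3 months = 72. The threshold is above 50% (section 6). The documents give neither the number of patients expected to be identified nor any rate of under-recording. Values for these below are assumptions, shown as a range.

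**1. Formula and pass limit.** Let E be patients enrolled and M the identified eligible patients recorded as not enrolled. Then 1a = E/(E + M), which exceeds 50% only if M < E. With E = 72:

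- M = 71: 72/143 = 50.3%, pass.
- M = 72: 72/144 = 50.0%, fail.

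**2. Direction of error in 1a.** If k non-enrolled patients go unrecorded, the reported value is E/(E + M − k), which is never below E/(E + M). In the extreme where none is recorded, it reads 72/72 = 100%.

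**3. Omissions that turn a fail into a pass.** With N truly identified and 72 enrolled, the omissions needed are N − 143, out of N − 72 non-enrolled.

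| Assumed N | True 1a | Omissions needed | Share of non-enrolled |
|---|---|---|---|
| 150 | 48% | 7 of 78 | 9% |
| 160 | 45% | 17 of 88 | 19% |
| 180 | 40% | 37 of 108 | 34% |
| 200 | 36% | 57 of 128 | 45% |

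**4. The reverse check.** Suppose C patients are counted and 1a passes. For the true result to be a fail, at least 144 − C patients must be missing, out of 72 non-enrolled.

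| Counted C | Reported 1a | Missing needed | Share of the 72 |
|---|---|---|---|
| 100 | 72% | 44 | 61% |
| 120 | 60% | 24 | 33% |
| 140 | 51% | 4 | 6% |

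A pass at 100 counted would take very heavy omission to overturn; a pass at 140 would not.

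**5. Direction of error in the refusal proportion.** With R refusals, the proportion is R/(E + M). Omitting k refusals gives (R − k)/(E + M − k), which is lower. Omitting k patients not enrolled for other reasons gives R/(E + M − k), which is higher. As an illustration, take N = 160 and assume 44 refusals (half of the 88): 44/160 = 27.5%. With 17 patients omitted it reads 27/143 = 18.9% if all 17 were refusals and 44/143 = 30.8% if none were.

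**The case against.** The best defence is that the plan does not contradict itself. Section 11.1 rules out only a formal log. Criterion 1a is confined to patients who were *identified*, so no census of ventilated patients is needed. Section 12.1 plainly intends some count, and a simple tally of surrogates contacted would fit the procedure described. The CRFs and the Study Monitoring Plan may contain one, and the lists of records in sections 16.3 and 18 are open-ended.

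All of that stands, and it sets the limits of the point. A reader might infer that 1a cannot be calculated, or that no count will be kept. The documents do not support either reading: they leave the source unnamed, which is different from forbidding one. The defence does not remove the need, though. Restricting the denominator to identified patients still requires that those identified but not enrolled be recorded, with a reason, and a primary criterion should have a stated data source.

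It is also fair to say that only the 143/144 limit comes from the plan, and that it holds only if exactly 72 are enrolled. The other counts are assumed, and nothing in the documents suggests the result will fall near 50%.

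**Conclusion.** The point holds as a gap in specification. Criterion 1a and the refusal proportion depend on a count for which the supplied text names no source, after setting aside the formal log that would normally provide it. Under-recording of non-enrolled patients can only favour a pass on 1a; its effect on the refusal proportion can go either way.

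The size depends on where the result falls. Near 50%, modest omissions decide the verdict: 17 of 88 in the assumed case of 160 identified. Far from 50%, they do not. A reader might go further and expect a false declaration of feasibility. The documents do not support that, because they give neither the number identified nor any sign of how complete informal recording would be.

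The effect is confined to these two figures. Accrual is observed directly, criteria 1b to 1d do not use this count, and the adoption choices open to sites in section 2.1 are not tied to 1a. Confidence is high that the supplied text names no source and moderate that none exists. This is a cheap improvement.

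**What to change.** - **Section 11.1.** Keep the instruction to find as many eligible patients as feasible. Replace only the clause that rules out a formal log with a one-line de-identified tally. Open the line when a patient is identified as eligible, before the surrogate's answer is known, and close it with the outcome: enrolled, surrogate refused, surrogate not reached, or other reason. The timing matters, because a tally filled in after the answer would allow the same one-sided omissions.
- **Sections 6 and 12.1.** State that the 1a denominator and the refusal proportion come from this tally. Report 1a as applying to identified patients only, since the tally does not remove selection in who gets identified. Leave the 50% threshold unchanged.
- **If a tally already exists** in the CRFs or monitoring plan, cite it in section 12.1 and confirm that entries are made at identification.

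The cost is a brief extra entry by existing therapists and coordinators, and a protocol amendment. Under section 16.1 that needs ethics board approval, and a revised Health Canada testing application if the approval refers to updated documents before initiation. The reported share may come out lower.
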